## 5.2 Listings

Number	Title
Listing 16.2.1.1.1	Listing of Subject Disposition at CRC Phase All Screened Subjects
Listing 16.2.1.1.2	Listing of Subject Disposition at Outpatient Phase All Screened Subjects
Listing 16.2.1.3	Listing of Qualification Criteria Status at CRC Phase All Screened Subjects
Listing 16.2.1.4	Listing of Analysis Population at CRC Phase All Screened Subjects
Listing 16.2.1.5	Listing of Analysis Population at Outpatient Phase All Screened

Number	Title
	Subjects
Listing 16.2.1.6	Listing of Subject Eligibility at CRC Phase All Screened Subjects
Listing 16.2.2.1	Listing of Protocol Deviations at CRC Phase All Screened Subjects
Listing 16.2.2.2	Listing of Protocol Deviations at Outpatient Phase All Screened Subjects
Listing 16.2.4.1.1	Listing of Subject Demographic and Baseline Characteristics Safety Population
Listing 16.2.4.1.2	Listing of Urine Pregnancy at CRC Phase All Screened Subjects
Listing 16.2.4.1.3	Listing of Urine Pregnancy at Outpatient Phase All Screened Subjects
Listing 16.2.4.2.1	Listing of Medical History All Screened Subjects
Listing 16.2.5.1	Listing of Study Drug Administration for CRC Phase ITT Population
Listing 16.2.5.2	Listing of Study Drug Administration for Outpatient Phase ITT Population
Listing 16.2.5.3	Listing of Prior Medication at CRC Phase Safety Population
Listing 16.2.5.4	Listing of Prior Medication at Outpatient Phase Safety Population
Listing 16.2.5.5	Listing of Concomitant Medication at CRC Phase Safety Population
Listing 16.2.5.6	Listing of Concomitant Medication at Outpatient Phase Safety Population
Listing 16.2.5.7	Listing of Rescue Medication at CRC Phase Safety Population
Listing 16.2.5.8	Listing of Rescue Medication at Outpatient Phase Safety Population
Listing 16.2.6.1.1	Listing of BGM Assessments at CRC Phase ITT Population
Listing 16.2.6.1.2	Listing of BGM Assessments at Outpatient Phase ITT Population
Listing 16.2.6.1.3	Listing of Exercise Sessions at CRC Phase ITT Population
Listing 16.2.6.1.4	Listing of Exercise Sessions at Outpatient Phase ITT Population
Listing 16.2.6.1.5	Listing of CGM Assessments at CRC Phase ITT Population
Listing 16.2.6.1.6	Listing of CGM Assessments at Outpatient Phase ITT Population
Listing 16.2.6.1.7	Listing of Draize Scale Scores at CRC Phase ITT Population
Listing 16.2.6.1.8	Listing of Injection Site Discomfort and Duration Results at CRC Phase ITT Population
Listing 16.2.6.1.9	Listing of Venous Blood Glucose (YSI Readings) at CRC Phase
Listing 16.2.6.1.10	Listing of Interstitial Glucose (IG) at CRC Phase ITT Population
Listing 16.2.6.1.11	Listing of Interstitial Glucose (IG) at Outpatient Phase ITT Population
Listing 16.2.6.1.12	Listing of Insulin Utilization at Outpatient Phase ITT Population
Listing 16.2.6.1.13	Listing of HbA1c ITT Population
Listing 16.2.7.1.1	Listing of Adverse Events at CRC Phase Safety Population
Listing 16.2.7.1.2	Listing of Adverse Events at Outpatient Phase Safety Population
Listing 16.2.8.1.1	Listing of Laboratory Results: Clinical Chemistry Safety Population
Listing 16.2.8.1.2	Listing of Laboratory Results: Hematology Safety Population
Listing 16.2.8.1.3	Listing of Laboratory Results: C-Peptide Safety Population
Listing 16.2.8.1.4	Listing of Laboratory Results: HIV Antibodies Safety Population

Number	Title
Listing 16.2.8.1.5	Listing of Urine Drug Screen Results Safety Population
Listing 16.2.9.1.1	Listing of Vital Signs at CRC Phase Safety Population
Listing 16.2.9.1.2	Listing of Vital Signs at Outpatient Phase Safety Population
Listing 16.2.9.2.1	Listing of Electrocardiogram (ECG) Results Safety Population
Listing 16.2.9.3.1	Listing of Physical Examination Findings Safety Population
Listing 16.2.9.3.2	Listing of Barriers to Physical Activity Diabetes (Type 1) (BAPAD-1) Results ITT Population
Listing 16.2.9.3.3	Listing of Hypoglycemia Fear Survey (HFS) Results ITT Population
Listing 16.2.9.3.4	Listing of Hypoglycemic Confidence Scale (HCS) Results ITT Population
Listing 16.2.10.1.1	Listing of General Comment Log All Screened Subjects

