7.4. Screen Failures

Screen failures are defined as participants who consent to participate in the clinical trial but are not subsequently randomized. A minimal set of screen failure information is required (demographics, inclusion/exclusion criteria, adverse event, protocol deviation, and date of screen failure) to ensure transparent reporting of screen failure participants, to meet the Consolidated Standards of Reporting Trials (CONSORT) publishing requirements and to respond to queries from regulatory authorities. Screen failures may be rescreened after a 30-day waiting period, at the discretion of the Investigator. Approximately 100 subjects may be screened to obtain 48 randomized subjects.

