12.4.8. Tabulation of Individual participant Data

Disposition, demographic, efficacy, and safety data will be listed as specified in the SAP. All eCRFs will have a corresponding listing of raw data reported.

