## 4. STATISTICAL METHODOLOGY

### 4.1 Definition of Analysis Population

**All Screened Subjects:** All Screened subjects will include any subject who signed the informed consent form.

**Intention to Treat (ITT) Population:** All randomized subjects regardless of whether they received Study Drug.

**Per Protocol (PP) Population:** ITT participants who completed a qualified exercise session, and who was dosed within the study window and did not meet any of the key exclusion criteria at screening. The definition of qualified exercise is defined in Section 2.4.

**Safety Population:** All randomized subjects who received any amount of Study Drug.

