#### **4.3.9 Safety Analysis**

##### **Adverse Events:**

All analyses will be conducted in the safety population. Adverse events will be recorded from the time of consent until completion of study. The number and percentage of subjects with AEs will be displayed by body system and preferred term (MedDRA), by study treatment. Summaries in terms of severity and relationship to Study Drug will also be provided. All SAEs will be summarized in a similar manner. Participant listings of all AEs causing discontinuation of study medication and SAEs will be produced.

All AEs will be listed for individual subjects showing both verbatim and preferred terms. Separate summaries of treatment emergent SAEs and TEAEs related to Study Drug will be generated.

AEs will be summarized separately during the CRC treatment visits. Any AE that occurs after administration of study drug at Visit 3 and prior to administration of the alternate study drug at Visit 4 will be treatment emergent with respect to the study drug received at Visit 3. Any AE that occurs after administration of study drug at Visit 4 and prior to the first administration of study drug in the out-patient phase will be treatment emergent for the study drug received at Visit 4. Any event reported on the eCRF that occurs at the time of or after the initiation of Study Drug in the out-patient phase is defined as treatment-emergent for that study drug. Additionally, an AE that was reported to have started on Day 1 without an associated onset time is assumed to have

occurred after the initiation of Study Drug. Hence, AEs occurring on Day 1 with no associated onset time are assumed to be treatment emergent.

SAEs associated with a protocol specified procedure and occurring after the time of consent but before administration of first dose of Study Drug are defined as Non-Treatment Emergent AEs (NTEAE).

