Table 14.3.1.6.2	Summary of Treatment-Emergent Adverse Events by System Organ Class, Preferred Term, Relationship to Study Drug and by Treatment at Outpatient Phase Safety Population
Table 14.3.1.7.1	Summary of Deaths due to Treatment-Emergent Adverse Events at

Number	Title
	CRC Phase Safety Population
Table 14.3.1.7.2	Summary of Deaths due to Treatment-Emergent Adverse Events at Outpatient Phase Safety Population
Table 14.3.1.8.1	Summary of Treatment-Emergent Adverse Events Leading to Study Discontinuation by MedDRA System Organ Class and Preferred Term at CRC Phase Safety Population
Table 14.3.1.8.2	Summary of Treatment-Emergent Adverse Events Leading to Study Discontinuation by MedDRA System Organ Class and Preferred Term at Outpatient Phase Safety Population
Table 14.3.2.1	Listing of Deaths at CRC Phase Safety Population
Table 14.3.2.2	Listing of Deaths at Outpatient Phase Safety Population
Table 14.3.2.3	Listing of Serious Adverse Events at CRC Phase Safety Population
Table 14.3.2.4	Listing of Serious Adverse Events at Outpatient Phase Safety Population
Table 14.3.2.5	Listing of Treatment-Emergent Adverse Events leading to Premature Discontinuation of Study Drug at CRC Phase Safety Population
Table 14.3.2.6	Listing of Treatment-Emergent Adverse Events leading to Premature Discontinuation of Study Drug at Outpatient Phase Safety Population
Table 14.3.4.1.1	Summary of Vital Signs at CRC Phase Safety Population
Table 14.3.4.1.2	Summary of Vital Signs at Outpatient Phase Safety Population
Table 14.3.4.2.1	Summary of Laboratory Data – Hematology Safety Population
Table 14.3.4.2.2	Summary of Laboratory Data – Clinical Chemistry Safety Population
Table 14.3.4.2.3	Summary of Abnormal Laboratory Findings Safety Population
Table 14.3.4.3.1	Summary of 12 Lead ECG Findings Safety Population
Table 14.3.4.3.2	Summary of Draize Scales at CRC Phase Safety Population
Table 14.3.4.3.3	Summary of Injection Site Discomfort and Duration at CRC Phase Safety Population
Table 14.3.4.4.1	Summary of Observed Laboratory Data: Shift from Baseline – Hematology Safety Population
Table 14.3.4.4.2	Summary of Observed Laboratory Data: Shift from Baseline – Clinical Chemistry Safety Population

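### A serious adverse event or death in a consented subject who is never dosed falls outside every planned adverse-event, SAE and death output, although the SAP undertakes to list all adverse events

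*SAP*

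**What the plan says.** SAP 4.3.9 (Safety Analysis, Adverse Events) makes four statements that bear on this point. Adverse events are recorded from consent. All of them will be listed by subject. All analyses use the safety population. And one group of pre-dose events gets its own name, NTEAE: "SAEs associated with a protocol specified procedure and occurring after the time of consent but before administration of first dose of Study Drug".

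SAP 4.1 defines the Safety Population as "All randomized subjects who received any amount of Study Drug". The same section defines All Screened Subjects as anyone who signed consent.

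The output titles in SAP 5.1 and 5.2 include "Listing of Adverse Events at CRC Phase Safety Population" (Listing 16.2.7.1.1), "Listing of Adverse Events at Outpatient Phase Safety Population" (Listing 16.2.7.1.2), "Listing of Deaths at CRC Phase Safety Population" (Table 14.3.2.1) and "Listing of Serious Adverse Events at CRC Phase Safety Population" (Table 14.3.2.3). The adverse-event summary tables 14.3.1.x and the other 14.3.2.x listings are on the same population.

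In the protocol, 7.4 names adverse events among the minimum data kept on a screen failure, and 12.4.8 adds: "All eCRFs will have a corresponding listing of raw data reported".

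**The concern.** The text of 4.3.9 and the output titles cannot both be followed. If events count from consent and all are to be listed, the listing must include people who consented but were never dosed. The Safety Population excludes them by definition.

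The NTEAE class makes the gap concrete. The SAP names a kind of pre-dose serious event, yet no output is titled for it, and a subject who has such an event and is then not dosed is outside every output where it could be shown. Whether a subject is covered can depend on the event itself, because an event that stops someone before Visit 3 dosing also takes that person out of the population.

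The period before dosing is not empty. It contains an overnight fast in insulin-pump users, sensor placement and, at Visit 3, glucose correction ahead of randomization (Protocol 10.1 to 10.3). What is at stake is a complete account of serious events in the study report. No efficacy result or between-arm comparison is affected.

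**Working it through.** There is no computed figure in the plan to reproduce on this point. The check traces each kind of subject through the population labels.

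**Step 1. Labels on the outputs (SAP 5.1, 5.2).**

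| Output | Population |
|---|---|
| Tables 14.3.1.1.1 to 14.3.1.8.2 (AE, SAE and death summaries) | Safety |
| Tables 14.3.2.1 to 14.3.2.6 (listings of deaths, SAEs, discontinuations due to AE) | Safety |
| Listings 16.2.7.1.1 and 16.2.7.1.2 (all AEs) | Safety |
| Listings of disposition, eligibility, deviations, medical history, comment log | All Screened |

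No adverse-event, SAE or death output is on All Screened or ITT, and none is titled for NTEAEs.

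**Step 2. Who is covered when an SAE occurs after consent and before the first dose.**

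| Subject | In Safety Population? | In an AE, SAE or death output? |
|---|---|---|
| Screen failure | No, not randomized | No |
| Eligible, leaves before Visit 3 | No, not randomized | No |
| Randomized at Visit 3, not dosed | No, not dosed | No |
| Dosed later | Yes | Yes, by the population label |

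A subject never dosed at a CRC visit does not reach the outpatient phase, so the CRC-phase outputs are the ones where the omission arises.

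**Step 3. Headcount.** Inputs: approximately 100 screened and 48 randomized (Protocol 7.4).

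- Consented, not randomized: 100 − 48 = 52.
- Share of those consented: 52 / 100 = 52%.
- Add any subject randomized but not dosed. The documents give no number. Randomization and dosing are consecutive steps of Visit 3 (Protocol 10.3.1), so few would be expected.

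**Step 4. Events.** The documents give no rate of adverse events between consent and first dose. The 52 therefore counts people, not events, and no expected number of omitted events follows from it.

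**Step 5. Deliberate or not.** SAP 4.4 declares no change from the protocol, and nothing in 4.3.9 says that events in undosed subjects are to be left out. A similar mismatch occurs elsewhere: 4.3.2 says HIV, C-peptide and urine drug screen results are listed for all screened subjects, while Listings 16.2.8.1.3 to 16.2.8.1.5 are titled for the Safety Population. That pattern suggests labels not reconciled with the text, rather than a decision to exclude events.

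**The case against.** The best case for leaving the plan alone is that the Safety Population is the usual base for adverse-event reporting, that Protocol 12.4.4 itself places all safety analyses on it, and that SAP section 5 calls its list anticipated and allows changes to bring it into line with the SAP text. A programmer who noticed the conflict could correct it without an amendment. This shows that the remedy is easy. It does not remove the conflict, because 4.3.9 contains both the undertaking to list every event and the restriction to the safety population, so the text alone does not settle which governs.

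Several stronger readings are tempting, and the documents do not support them.

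- *That such an event appears nowhere.* Disposition and eligibility listings cover all screened subjects and give reasons for discontinuation or screen failure (SAP 4.3.1, Disposition), and the comment log is also all-screened. A reason or remark may appear there. Nothing says these listings carry the event term, seriousness, severity or causality.
- *That it goes unreported.* Protocol 9.3.1.6 requires every SAE, whatever its cause, to reach the sponsor within 24 hours of the investigator's knowledge of it, and the SAE form must agree with the eCRF. The gap is in the study report.
- *That NTEAE means an event that prevents dosing, or that only mild ones would be listed.* The definition has no condition about dosing, and it covers only procedure-associated SAEs. A subject dosed later is within the population. All are serious by definition, and Protocol 9.3.1.3.1 separates seriousness from severity.
- *That the SAP's precedence clause cancels the protocol's screen-failure reporting.* Protocol 7.4 requires the data to be collected, and nothing in the SAP stops that. Protocol 12.4.8 leaves the specification of listings to the SAP, and its sentence on eCRFs names no population.

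**Conclusion.** The point holds as a minor inconsistency. Following the output labels as written, an SAE or death after consent in a never-dosed subject would be in no adverse-event, SAE or death table or listing, contrary to the undertaking in SAP 4.3.9 to list all adverse events.

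Its size can be given only as coverage: about 52 of roughly 100 consented subjects, plus any randomized but not dosed. This rests on the protocol's approximate screening figure and on nearly all randomized subjects being dosed. A reader might take the 52 as a measure of lost safety data. It is not one, since most of these people may have no event at all. Sample size, alpha, power, efficacy analyses and between-arm safety tables do not change.

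**What to change.** 1. In SAP 5.1 and 5.2, change the population of Listing 16.2.7.1.1 and Tables 14.3.2.1 and 14.3.2.3 to All Screened Subjects, with a not-dosed entry in the treatment column and a flag for pre-dose events and NTEAEs. Alternatively, leave them and add one listing of pre-dose adverse events, SAEs and deaths on All Screened Subjects.
2. In SAP 4.3.9, reword the population sentence so that summary tables use the Safety Population and the listings of adverse events, SAEs and deaths cover all screened subjects. Without this, the new labels would contradict the text.
3. Keep the 14.3.1.x percentage tables on the Safety Population, so that denominators and treatment comparisons stay as planned.

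The cost is a short SAP edit and minor programming for the not-dosed entry and the flag. The protocol already requires the data, so collection does not change.

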### 5.3 Figures

Number	Title
Figure 14.2.1.1.1	Bar Diagram for Mean Incidence Rate by Treatment in CRC Phase ITT Population
Figure 14.2.1.1.2	Bar Diagram for Mean Incidence Rate by Treatment in CRC Phase PP Population
Figure 14.2.1.2.1	Bar Diagram for Mean Incidence Rate by Treatment in Outpatient Phase ITT Population
Figure 14.2.1.2.2	Bar Diagram for Mean Incidence Rate by Treatment in Outpatient Phase PP Population
